AMPP	American Migraine Prevalence and Prevention
AP	Alkaline phosphatase
AST	Aspartate aminotransferase
BP	Blood pressure
bpm	Beats per minute
BPPV	Benign paroxysmal positional vertigo
BUN	Blood urea nitrogen
CAD	Coronary artery disease
CBC	Complete blood count
CD	Compact disc
CFR	Code of Federal Regulations
CRF	Case Report Form
CRO	Contract research organization
CS	Clinically significant
C-SSRS	Columbia Suicide Severity Rating Scale
DBP	Diastolic blood pressure
DVD	Digital video disc
e-diary	Electronic diary
ECG	Electrocardiogram
EoS	End of study
FDA	Food and Drug Administration
GCP	Good Clinical Practice
HEENT	Head, eyes, ears, nose, and throat
HIPAA	Health Insurance Portability and Accountability Act
HIV	Human immunodeficiency virus
HR	Heart rate
IB	Investigator's Brochure
ICF	Informed Consent Form
ICH	International Conference on Harmonization
ICHHD	International Headache Classification
IHS	International Headache Society
IUD	Intrauterine Device
IV	Intravenous
ITT	Intent-to-treat
IVRS	Interactive Voice Response System
IWR	Interactive Web Response
L	Lasmiditan
MBS	Most Bothersome Symptom
MedDRA	Medical Dictionary for Regulatory Activities

mg	milligram
MIDAS	Migraine disability assessment
mITT	modified Intent-to-treat
mL	milliliter
mmHg	millimeters of mercury
NCS	Not clinically significant
P	Placebo
PP	Per protocol
RR	Respiratory rate
SAE	Serious adverse event
SBP	Systolic blood pressure
SD	Standard deviation
TEAE	Treatment emergent adverse events
WBC	White blood cells
WHO	World Health Organization
WOCBP	Women of child-bearing potential
WNL	Within normal limits

1 PURPOSE

This Statistical Analysis Plan was defined by the Sponsor and the responsible statistician without knowledge of the randomization code. It is based on the Study Protocol (Final Version 1.0, November 30, 2015). It contains an actualization and specification of the statistical methods described therein.

2 SUMMARY OF THE CLINICAL TRIAL PROTOCOL

2.1 Study Summary

This is a prospective, randomized, double-blind, placebo-controlled study in subjects with disabling migraine (MIDAS score ≥ 11). Approximately 2968 subjects will be screened and randomized (742 per treatment group based on the first dose) to ensure that approximately 2280 subjects (570 per treatment group based on the first dose) treat a migraine attack and complete the Treatment Period.

[figure not shown]
Subjects will be asked to treat a migraine attack with study drug on an outpatient basis. Subjects will be provided with a dosing card containing a dose for initial treatment and a second dose to be used for rescue or recurrence of migraine. Each dose consists of two tablets. Each subject's study participation will consist of a screening visit (Visit 1) with a telephone contact within 7 days to confirm eligibility, a Treatment Period of up to 8 weeks, and an EoS visit (Visit 2) within one week (7 days) of treating a migraine attack. The total time on study will be approximately 11 weeks. Subjects will be randomly assigned treatment as described in Section 2.3.

Subjects will be asked to treat their next migraine attack within 4 hours of onset provided that the headache severity is documented as being of mild, moderate, or severe intensity at that time and not improving. Subjects will record their response to the first dose over the next 48 hours using an electronic diary (e-diary). Subjects will be asked not to use rescue medication until at least 2 hours after dosing with study drug and completing the 2 hour assessments. If the migraine does not respond at 2 hours, a second dose of study drug may be taken up to 24 hours after the first dose as long as no other rescue medication has been used. If the migraine does respond within 2 hours (headache becomes pain-free) but then recurs after 2 hours a second dose of study drug may be taken up to 24 hours after the first dose. Subjects will record their response to a second dose, taken for either rescue or recurrence, for 48 hours in the e-diary. The total time for recording response to study drug is up to 72 hours depending on whether or not a second dose is used. Subjects are to contact the clinic to schedule EoS/Visit 2 within one week (7 days) after one attack has been treated, or after 8 weeks have passed without treating an attack. The total time on study is approximately 11 weeks.

This study is designed to evaluate the efficacy and safety of lasmiditan 50 mg, of lasmiditan 100 mg and of lasmiditan 200 mg, each compared with placebo, in the acute treatment of migraine based on the first dose.

The study will be conducted at up to 150 centers in the US, United Kingdom (UK) and Germany.

Study schema:

2.2 Sample Size

This Phase 3 study is designed to demonstrate that lasmiditan is effective in the treatment of acute migraine in adult subjects with and without aura. The sample size was estimated based on the 2-hour headache pain-free and associated symptoms-free response rates observed in the Phase 2 study COL MIG-202.

Dose	Pain-free	Nausea-free	Phonophobia-free	Photophobia-free
Placebo	7.4%	59.3%	51.9%	36.4%
50 mg	13.9%	68.4%	58.2%	53.2%
100 mg	13.6%	74.1%	75.3%	67.9%
200 mg	18.8%	63.8%	59.4%	58.0%

For the primary endpoint of subjects pain-free at 2 hours, a sample size of 570 evaluable subjects per arm provides power of >90% for the 50 mg dose, the 100 mg dose and the 200 mg dose.

In order to estimate sample size for the key secondary endpoint of subjects who were Most Bothersome Symptom (MBS)-free at 2 hours, simulation was performed in SAS on the conditional probability of being free from any one symptom defined as MBS under 4 different scenarios. For each symptom or combination of symptoms, the likelihood of an individual symptom being the MBS was estimated. In the most conservative scenario (Scenario 1) it was assumed that nausea would always be declared the MBS if it was present, regardless of the presence of other symptoms (phonophobia or photophobia). The other 3 scenarios assumed lower likelihoods of nausea to be considered the MBS and allowed for the other symptoms (either phonophobia or photophobia) to be considered the MBS at a higher rate. This resulted in power estimates of > 95% for MBS at a sample size of 570 for the lasmiditan 50 mg dose and >99% for MBS at sample sizes of 450 to 570 per arm for the 100 mg dose across all 4 scenarios. For the 200 mg dose, an average power of 71% was estimated across five seeds under the most conservative Scenario 1. In contrast, the 3 scenarios that did not declare nausea to be the default MBS if it was present estimated a greater average power of 82.6% to 91%.

Group	Scenario	Variable	Seed				
			55405	74951	82002	82377	90075
Placebo vs D50	1	Power (MBS)	96.90%	95.90%	96.10%	95.60%	96.80%
		Sample Size	570	570	570	570	570
	2	Power	93.70%	94.30%	94.80%	93.90%	93.90%
		Sample Size	450	450	450	450	450
	3	Power	90.40%	90.40%	90.10%	91.00%	91.40%
		Sample Size	575	575	575	575	575
	4	Power	93.70%	94.30%	94.80%	93.90%	93.90%
		Sample Size	450	450	450	450	450
Placebo vs D100	1	Power (MBS)	>99.99%	>99.99%	>99.99%	>99.99%	>99.99%
		Sample Size	570	570	570	570	570
	2	Power	99.90%	>99.99%	>99.99%	>99.99%	>99.99%
		Sample Size	450	450	450	450	450
	3	Power	>99.99%	>99.99%	>99.99%	>99.99%	>99.99%
		Sample Size	575	575	575	575	575
	4	Power	99.90%	>99.99%	>99.99%	>99.99%	>99.99%
		Sample Size	450	450	450	450	450
Placebo vs D200	1	Power	70.87%	70.87%	72.97%	71.17%	68.47%
		Sample Size	570	570	570	570	570
	2	Power	84.40%	85.00%	85.80%	85.90%	85.80%
		Sample Size	450	450	450	450	450
	3	Power	83.50%	83.20%	81.30%	83.40%	81.80%
		Sample Size	575	575	575	575	575
	4	Power	90.20%	90.50%	92.50%	91.40%	90.40%
		Sample Size	450	450	450	450	450

It is expected for a one-sided, two-sample comparison of proportions at the 2.5% level of significance, a sample size of 570 subjects per treatment group (as defined by the first dose) provides >90% power to detect a difference in headache pain-free response rates for assumed true rates of 7.4% and 18.8% (placebo and 200 mg), 7.4% and 13.6% (placebo and 100 mg), and 7.4% and 13.9% (placebo and 50 mg) >90 % power for MBS for both the 50 mg dose arm and the 100 mg dose arm and very near or higher than 80% power for MBS in the 200 mg dose arm.

2.3 Randomization

Subjects will be centrally randomized to one of 7 treatment sequences to receive lasmiditan 50 mg (L50 mg), lasmiditan 100 mg (L100 mg) or lasmiditan 200 mg (L200 mg) or placebo (P) for the first dose (in a 1:1:1:1 ratio) and a second dose for rescue or recurrence of migraine (if needed). Subjects will be stratified (yes or no) for current use of concomitant medication(s) that reduce the frequency of migraine episodes. Study drug will be randomized and dispensed at Visit 1 as follows:

First dose for treatment of migraine	Second dose for rescue or recurrence of migraine (if needed)
L50 mg	L50 mg
	L50 mg
	placebo
L100 mg	L100 mg
	L100 mg
	placebo
L200 mg	L200 mg

	L200 mg
	placebo
Placebo	placebo

3 EFFICACY AND SAFETY ENDPOINTS

3.1 Primary Efficacy Endpoint

The primary efficacy endpoint is the treatment comparison, between lasmiditan 200 mg and placebo, as measured by subjects who are headache pain-free at 2 hours post first dose.

3.2 Key Secondary Efficacy Endpoint

- Treatment comparison, between lasmiditan 200 mg and placebo, as measured by subjects who are MBS-free at 2 hours post first dose.
- Treatment comparison, between lasmiditan 100 mg and placebo, as measured by subjects who are headache pain-free at 2 hours post first dose.
- Treatment comparison, between lasmiditan 100 mg and placebo, as measured by subjects who are MBS-free at 2 hours post first dose.
- Treatment comparison, between lasmiditan 50 mg and placebo, as measured by subjects who are headache pain-free at 2 hours post first dose.
- Treatment comparison, between lasmiditan 50 mg and placebo, as measured by subjects who are MBS-free at 2 hours post first dose.

3.3 Exploratory Efficacy Endpoints

- Headache pain-free at 0.5, 1, 1.5, 3, 4, 24, and 48 hours post-dose based on first dose
- Sustained headache pain-free at 24 and 48 hours post-dose based on first dose
- MBS-free at 0.5, 1, 1.5, 3, 4, 24, and 48 hours post-dose based on first dose
- Presence of migraine symptoms (nausea, phonophobia, photophobia, vomiting) at all-time points based on first and second dose
- Headache relief at all time points based on first dose
- MBS-free at 0.5, 1, 1.5, 2, 3, 4, 24, and 48 hours post-dose by chosen MBS based on first dose
- Time to headache pain-free through 24 hours after first dose
- Time to headache relief through 24 hours after first dose
- Time to MBS-free through 24 hours after first dose, overall and separately for each symptom
- Disability at all time points based on elapsed times since first and second doses
- Incidence of rescue or recurrence medication use at 2 hours, between 2 and 24 hours, and between 24 and 48 hours post first dose
- Incidence of headache recurrence
- Patient global impression of change (PGIC) scale at two hours post-dose, based on elapsed times since first and second dose
- Headache pain-free after a second dose, separately for rescue and recurrence, at all time points
- Time to headache pain-free through 24 hours after a second dose, separately for rescue and recurrence

- Headache relief after a second dose, separately for rescue and recurrence, at all time points
- Time to headache relief through 24 hours after a second dose, separately for rescue and recurrence
- MBS-free after a second dose, separately for rescue and recurrence, at all time points, overall and separately for each symptom
- Time to MBS-free through 24 hours after a second dose, separately for rescue and recurrence, overall and separately for each symptom

3.4 Safety Endpoints

- Adverse events
- Physical examination
- Vital signs
- 12-lead electrocardiograms
- Clinical laboratory parameters
- Columbia Suicide Severity Rating Scale (C-SSRS)

3.5 Resource Utilization Endpoints

- Visits to a cardiologist, or any procedures, hospitalizations, new treatments, or adjustments to treatments for any cardiovascular conditions or disease
- Visits to an emergency room or urgent care for treatment of migraine

4 ANALYSIS POPULATIONS

The following analysis populations will be defined for this study. Subjects' inclusion in or exclusion from these analysis populations will be finalized prior to study unblinding

Randomized population	All randomized subjects. Subjects will be evaluated by the drug to which they are randomized.
Safety population	All randomized subjects who use at least one dose of study drug, regardless of whether or not they undergo any study assessments. Subjects will be evaluated by the drug they use, not by the drug to which they are randomized, when data indicate a difference.
ITT population	All randomized subjects who use at least one dose of study drug and have any post-dose headache severity or symptom assessments. Subjects are evaluated by the drug to which they are randomized.
mITT population	All ITT subjects who treat a migraine attack within four hours of onset. Subjects will be evaluated by the drug to which they are randomized. The mITT population is the primary analysis population.
PP population	All mITT subjects will be considered per protocol (PP) if they do not have major protocol deviations, enumerated below, which might impact the assessment of efficacy. Subjects will be evaluated by the drug to which they are randomized.

Safety-2nd Dose population	All randomized subjects who were considered in the safety population after the first dose and use a second dose of study drug, regardless of whether or not they undergo any study assessments. Subjects will be evaluated by the drug they use, not by the drug to which they are randomized.
ITT-2nd Dose population	All randomized subjects who were considered ITT after the first dose and use a second dose of study drug and have any post-dose headache severity or symptom assessments. Subjects will be evaluated by the drug to which they are randomized.

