The bioavailability of lasmiditan 200 mg administered orally as a tablet formulation under fed and fasted conditions was investigated (clinical study COL MIG-104). A slight delay in the time to reach maximum plasma concentration was observed in the fed state. As in other Phase 1 studies, lasmiditan was well tolerated. The most common AEs across both conditions were somnolence, dizziness, orthostatic hypotension (with and without dizziness) and paresthesia.

The efficacy of oral lasmiditan in the acute treatment of migraine was evaluated in a Phase 2 double-blind, placebo-controlled, parallel-group dose-ranging study conducted in five European countries (clinical study COL MIG-202). A total of 391 subjects treated a single migraine attack at home using one of four doses of lasmiditan (50, 100, 200 or 400 mg) or placebo. The proportion of patients with headache relief (moderate or severe headache becoming mild or none) or who were pain free showed statistically significant dose responses at 2 hours after treatment. Associated symptoms such as nausea, phonophobia and photophobia also responded to lasmiditan. There were no clinically significant changes in clinical laboratory parameters, ECGs or vital signs.

Treatment-emergent adverse events (TEAEs) were reported by 22% of the subjects receiving placebo and by 65, 73, 86 and 84% of subjects receiving 50, 100, 200 and 400 mg lasmiditan,

respectively. The most common adverse events seen in the lasmiditan groups were related to the nervous system. These included dizziness, fatigue, vertigo, somnolence and paresthesia. Chest symptoms characteristic of triptan use were rare and occurred with a similar frequency in the placebo and active groups.

During the clinical development of lasmiditan there were no deaths and no subjects were withdrawn due to adverse events. One serious adverse event (SAE) of moderate dizziness leading to overnight hospitalization was reported in the oral dose-ranging study. This occurred in a female patient given 200 mg lasmiditan, and resolved without sequelae.

More details on the preclinical and clinical experience with lasmiditan are given in the Clinical Investigator's Brochure. 

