## 10.3 Analysis Populations

### 10.3.1 Primary efficacy – FIRST dose

The statistical analysis of the first dose will be based on the analysis populations as defined below:

Safety population	All randomized subjects who use at least one dose of study drug, regardless of whether or not they undergo any study assessments. Subjects are evaluated by the drug they use, not by the drug to which they are randomized.
ITT population	All randomized subjects who use at least one dose of study drug and have any post-dose assessments. Subjects are evaluated by the drug to which they are randomized.
mITT population	All randomized subjects who use at least one dose of study drug to treat a qualifying migraine attack and have any post-dose assessments. Subjects are evaluated by the drug to which they are randomized.

**PP population** All ITT subjects will be considered per protocol (PP) if they dose a migraine attack and do not deviate from the protocol.

The following is a list of additional protocol violations which would exclude subjects from the PP population:

- Subject received excluded rescue medications or used rescue medication before 2 hour time point.
- Subject used recurrence medication before 2 hour time point.
- Subject did not receive study drug as assigned.
- Subject did not meet all inclusion/exclusion criteria.
- Subject did not treat a migraine of at least moderate severity.

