#### **10.5.2 Sensitivity Analyses of the Primary and Key Secondary Endpoints**

The primary endpoint of pain free at 2 hours and the key secondary endpoint of MBS free are defined as proportions. The prespecified approach for handling missing data is to assume that subjects with missing data are nonresponders. While this approach is appropriately conservative, a sensitivity analysis will be incorporated to exclude subjects with missing data.

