5.3 Handling of Missing Values

Subjects who fail to record information at a particular analysis time point will have that value considered missing in the respective table, unless otherwise specified.

The primary and key secondary endpoints of headache severity and MBS presence at 2 hours post-dosing are two exceptions to this: (1) Subjects who fail to record a headache severity at 2 hours will be assumed to have not achieved headache pain-free, and (2) subjects who fail to record the absence of a symptom at 2 hours that was considered their MBS at baseline will be assumed to have not achieved MBS-free. A sensitivity analysis for missing data under alternative assumptions will be performed, as described in Section 11.5.

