1. Retroactive dose entry. If a subject enters the time of a dose retroactively, rather than at the time of taking the dose, the recorded time, and potentially date, of the second dose may be before some or all of the scheduled times of assessments that would otherwise have appeared to be associated with the first dose. In those cases, the apparent first-dose assessments after the recorded time of the second dose, and the second-dose assessments at times calculated from the retroactively entered dosing time will not be included in efficacy analyses.
2. Reports intention to take second dose, without confirmation. Subjects report their intention to take a second dose but may not *confirm* having done so in e-diary. Even if indications of taking second dose are observed in e-diary data, until the entry shows confirmation of second dose times, the e-diary will not have a confirmed second-dose time from which to calculate post-dose assessment times after that second dose, and it will not switch to second-dose mode. In this state, second-dose assessments will be missing. Additionally e-diary continues to collect first dose data although the subject may have taken second dose. Even if use of a second dose is recorded on the on CRF, the related second-dose assessments may not be available in the e-diary because the e-diary is not working in second-dose mode; hence, the exploratory endpoints for second dose will not

be available at those analysis times. Additionally, first dose assessments collected after this time will be considered unscheduled.

3. Multiple reports of a migraine - complicated by aura. If a subject reports a migraine, but does not indicate taking first dose at a specific time due to presence of aura, the efficacy and exploratory analysis endpoints for first and second dose will be summarized for the migraine, which has the reference for most recent available treated migraine data at analysis time points.
4. Missing first dose dates and associated assessments in e-diary. If the first dose is reported taken in the CRF with the appropriate date entered in CRF but the subject did not complete the e-diary for assessments, then the date of first dose and associated assessments will be missing in e-diary data. These subjects (e.g. lost to follow-up) will not be included in appropriate populations of efficacy analysis.

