11.3 Key Secondary Efficacy Analysis

The key secondary efficacy analyses will test the following:

- The treatment effect, between lasmiditan 200 mg and placebo, of the key secondary efficacy endpoint of MBS-free at 2 hours post-dose.
- The treatment effect, between lasmiditan 100 mg and placebo, of the key secondary efficacy endpoint of headache pain-free at 2 hours post-dose.
- The treatment effect, between lasmiditan 100 mg and placebo, of the key secondary efficacy endpoint of MBS-free at 2 hours post-dose.
- The treatment effect, between lasmiditan 50 mg and placebo, of the key secondary efficacy endpoint of headache pain-free at 2 hours post-dose.
- The treatment effect, between lasmiditan 50 mg and placebo, of the key secondary efficacy endpoint of MBS-free at 2 hours post-dose.

MBS-free is defined as the absence of the associated symptom of migraine (either nausea, phonophobia, or photophobia) at 2-hour post-dose that was identified pre-dose as the most bothersome symptom. Subjects who record that no symptoms were present at baseline will be

excluded from the key MBS analyses. Likewise, subjects who treat a migraine of no (0) severity will not be included in the key analysis of headache pain. Such subjects will also be excluded from the table produced for the sensitivity analysis described in Section 11.5, but not from the programming steps that impute missing MBS data.

Subjects who do not provide a symptom rating at baseline will be considered as follows:

- Subjects who record at least one symptom present at baseline, but who do not designate one as most bothersome, will be treated as if all symptoms present are most bothersome and will be considered MBS-free at any time point post-dose only if all symptoms present at baseline are no longer present at that time point.

Subjects taking rescue medication within the first two hours, or who fail to record a symptom rating at 2 hours, will be assumed to have not achieved MBS-free. Subjects who use other medication prior to the study drug to treat the migraine attack will also be assumed to have not achieved MBS-free.

The counts and percentages of which symptom was chosen as the most bothersome symptom will also be presented.

These analyses will be presented by treatment group, based on the first dose.

Sensitivity analyses, as described in Sections 11.4, 11.5 and 11.6 will also be performed for the key secondary endpoints on the mITT population.

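### Dosed subjects with no post-dose headache or symptom entry drop out of ITT and mITT instead of counting as non-responders, and no planned analysis tests the effect

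*SAP*

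**What the plan says.** **Entry to the populations.** SAP Section 4 defines ITT as "All randomized subjects who use at least one dose of study drug and have any post-dose headache severity or symptom assessments" and mITT as "All ITT subjects who treat a migraine attack within four hours of onset". Anyone outside ITT is therefore outside the primary population. Protocol Section 10.3.1 already had a condition of this kind, "All randomized subjects who use at least one dose of study drug and have any post-dose assessments". The SAP narrows it to severity or symptom entries, and its list of changes (Section 5.1) does not mention the narrowing.

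**No diary at all.** SAP Section 5.4, Scenario 4, covers subjects whose CRF reports a first dose but who did not complete the e-diary: "These subjects (e.g. lost to follow-up) will not be included in appropriate populations of efficacy analysis".

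**Missing 2-hour data inside the populations.** Protocol Section 10.5.2 states: "The prespecified approach for handling missing data is to assume that subjects with missing data are nonresponders". SAP Section 5.3 applies this to pain, "Subjects who fail to record a headache severity at 2 hours will be assumed to have not achieved headache pain-free", and Section 11.3 to the most bothersome symptom (MBS): subjects who take early rescue "or who fail to record a symptom rating at 2 hours, will be assumed to have not achieved MBS-free".

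**Sensitivity analyses.** SAP Sections 11.2 and 11.3 place the analyses of Sections 11.4, 11.5 and 11.6 on mITT. Section 11 repeats the primary and key secondary analyses on ITT and per-protocol.

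**The concern.** Take two subjects who both dose within 4 hours and both lack a 2-hour value. One made a single entry at 30 minutes, or first answered at 24 hours, and is analysed as a failure. The other made no entry and is not analysed. The 2-hour outcome is equally unknown for both; one entry at some other time decides how each is treated.

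This selection takes place after randomisation and after dosing, so randomisation does not protect it. If silence is commoner on lasmiditan and silent subjects did not respond, the active response rates are too high and the one-sided error rate exceeds 2.5%. If silence is commoner on placebo, the comparison is biased against the drug. SAP Section 11.5 recognises that missing data may differ by arm, but it works only on subjects who have already met the entry condition.

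**Working it through.** **1. Can any planned analysis bring these subjects back?**

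| Analysis | Population | Restores silent dosers? |
|---|---|---|
| Primary and key secondary (SAP 11.2, 11.3) | mITT | No |
| Repeats (SAP 11) | ITT, per-protocol | No: same entry condition |
| Corrected stratum (SAP 11.4) | mITT | No |
| Multiple imputation (SAP 11.5) | mITT | No: imputes only for subjects already in mITT |
| Complex e-diary data (SAP 11.6) | mITT | No: removes more subjects |
| Sensitivity analysis in Protocol 10.5.2 | Excludes subjects with missing data | No |

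The Safety population keeps them, but it is not used for efficacy.

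**2. The plan's own power figure.** Inputs from SAP Section 2.2: 570 per arm, one-sided 0.025, pain-free rates 7.4% (placebo), 13.9% (50 mg), 13.6% (100 mg), 18.8% (200 mg); stated power above 90% for each dose.

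Power = Φ[(p1 − p0 − 1.96·SE0)/SE1], where SE0 uses the pooled rate and SE1 the separate rates. For 100 mg, SE0 = √(2 × 0.105 × 0.895/570) = 0.01816 and SE1 = √((0.136 × 0.864 + 0.074 × 0.926)/570) = 0.01807, so Φ[(0.062 − 0.0356)/0.01807] = 92.8%. The same formula gives 94.6% for 50 mg and above 99.9% for 200 mg. The stated figure reproduces.

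**3. Restoring silent dosers as failures.** Let e be the share of dosed subjects with no post-dose severity or symptom entry. The documents give no value, so every e below is an assumption. The restored rate is p(1 − e) and the restored arm size is 570/(1 − e). For placebo 1% and active 3%:

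- placebo: 0.074 × 0.99 = 7.33%
- 100 mg: 0.136 × 0.97 = 13.19%, difference 5.87 points (was 6.2)
- 200 mg: 0.188 × 0.97 = 18.24%, difference 10.91 points (was 11.4)

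| e placebo / active | 50 mg difference, power | 100 mg difference, power | 200 mg difference, power |
|---|---|---|---|
| 0 / 0 | 6.50, 94.6% | 6.20, 92.8% | 11.40, >99.9% |
| 1% / 3% | 6.16, 93.1% | 5.87, 91.0% | 10.91, >99.9% |
| 2% / 5% | 5.95, 92.2% | 5.67, 90.0% | 10.61, >99.9% |
| 5% / 5% | 6.18, 94.5% | 5.89, 92.7% | 10.83, >99.9% |
| 2% / 10% | 5.26, 86.6% | 4.99, 83.3% | 9.67, 99.9% |
| 5% / 2% | 6.59, 96.2% | 6.30, 94.8% | 11.39, >99.9% |

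**4. Direction.** Restoring changes the difference by p0·e0 − p1·e1. Equal silence shrinks the absolute difference slightly but leaves the rate ratio p1/p0 and, as the 5% / 5% row shows, power almost unchanged. The rate ratio moves in the drug's favour as soon as placebo silence is the higher. The absolute difference does so only when e0/e1 exceeds p1/p0: 13.6/7.4 = 1.8 for 100 mg, 13.9/7.4 = 1.9 for 50 mg, 18.8/7.4 = 2.5 for 200 mg. That is why 5% / 2% (ratio 2.5) raises the two lower-dose differences and leaves 200 mg level.

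**5. One-sided error.** Suppose the true rates among all dosed subjects are equal and all silent subjects are non-responders. The analysed rate is then p/(1 − e). With 570 analysed per arm, the formula in step 2 gives:

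| e placebo / active | True rate 7.4% | True rate 34.6% |
|---|---|---|
| equal | 2.5% | 2.5% |
| 1% / 3% | 3.1% | 4.4% |
| 2% / 5% | 3.5% | 5.9% |
| 2% / 10% | 6.2% | 19.4% |
| 5% / 2% | 1.7% | 0.9% |

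The 34.6% is the Phase 2 placebo photophobia-free rate in Protocol Section 10.1 (SAP Section 2.2 prints 36.4%). It stands in for an MBS rate and is only an illustration.

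**The case against.** **The exclusion is narrow.** The diary prompts, with alarms, at eight times from 0.5 to 48 hours. One severity or symptom answer at any of them keeps a subject in ITT, and in mITT if the dose was within 4 hours. A subject who sleeps through the first four hours and answers at 24 hours is already a failure. This stands. A reader might infer that everyone who stopped recording or was lost is removed; the documents do not support that.

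**Sedation is an inference.** A reader might infer that the drug's own effects cause the silence. Protocol Section 4.2 describes the common events as mainly nervous-system: "These included dizziness, fatigue, vertigo, somnolence and paresthesia". It gives Phase 2 treatment-emergent event rates of 22% on placebo and 65% to 86% across the doses. But Section 4.3 calls the frequent events transient and usually mild or moderate, Section 4.2 reports no withdrawals due to adverse events, and nothing links these events to missing entries. The link is possible, but it cannot fix the direction of bias.

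**No strict contradiction.** Protocol Section 10.5.1 applies the non-responder rule within the ITT and mITT analyses, the entry condition comes from the protocol, and membership is settled before unblinding. This also stands. The populations are a debatable choice applied consistently. What remains is that like cases are treated differently and the effect is untested.

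**The gap will be visible.** SAP Section 6 reports treated, Safety, ITT and mITT counts by treatment sequence, so Safety minus ITT can be derived. It does not separate silent dosers who would otherwise have met the 4-hour rule, and no efficacy analysis uses it.

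**An all-dosed analysis mixes two changes.** It also brings in subjects who dosed after 4 hours. This is right, and the main added analysis should keep the 4-hour rule.

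**Conclusion.** The point holds in a limited form. Dosed subjects with no post-dose severity or symptom entry leave ITT and mITT, those with a single entry and no 2-hour value count as failures, and no planned analysis tests the difference.

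Direction and size are unknown. A reader might conclude that lasmiditan's effect is biased upward, but that needs more silence on active drug and silent subjects who truly failed, and the documents establish neither. Under the assumed 3% active and 1% placebo, the pain-free differences fall by 0.3 points (50 and 100 mg) and 0.5 points (200 mg), and error among equal arms rises from 2.5% to 3.1% at a 7.4% response rate. The 200 mg pain-free comparison keeps 99.9% power or more throughout the assumed range. The 100 mg comparison falls to about 90% power at 2% / 5% and to 83.3% at 2% / 10%. At a given imbalance, error rises more at the higher response rate used to illustrate MBS.

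This does not call for new population definitions. It is a cheap improvement.

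**What to change.** Keep mITT as the primary population and leave Protocol Section 10.3.1 unchanged. In the SAP, before unblinding:

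1. Add to Section 11.5 a sensitivity analysis of the six confirmatory comparisons in all dosed subjects with a recorded onset-to-dose time within 4 hours, using the same logistic model. Count subjects with no post-dose entry as not pain-free and, where baseline symptoms were recorded, as not MBS-free. Under Protocol Section 9.1.8, onset and dosing times are diary items that do not depend on post-dose entries.
2. Add a matching ITT version in all dosed subjects that counts Scenario 4 subjects as failures. They have no diary onset time, so they belong in this version only. For MBS they have no recorded baseline symptom; state that they count as failures, in line with Protocol Section 10.7, which assumes that all symptoms are present when baseline severity is missing.
3. In Section 6, report dosed-but-excluded subjects by first-dose arm, separating those with a diary onset and dose time from Scenario 4 subjects.
4. List the narrower ITT wording in Section 5.1.

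The cost is SAP text and a few extra tables. Response rates in the added analyses may be slightly lower.
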